8.5 Pregnancy

All pregnancies and outcomes of pregnancy should be reported to the sponsor and AstraZeneca.

8.5.1 Maternal exposure

If a patient becomes pregnant during the course of the study IP should be discontinued immediately.

Pregnancy itself is not regarded as an AE unless there is a suspicion that the IP under study may have interfered with the effectiveness of a contraceptive medication. Congenital abnormalities/birth defects and spontaneous miscarriages should be reported and handled as SAEs. Elective abortions without complications should not be handled as AEs. The outcome of all pregnancies (spontaneous miscarriage, elective termination, ectopic pregnancy).

If any pregnancy occurs in the course of the study, then the Investigator or other site personnel informs the sponsor's representatives within 1 day of when he/she became aware of it.

8.6 Overdose

Dapagliflozin has been well tolerated at doses of up to 500 mg/day in single dose testing in healthy volunteers and up to 100 mg/day in repeat dose testing for 14 days in healthy volunteers and patients with T2D. Suspected single intake of less than 50 tablets of 10 mg dapagliflozin tablets or repeated intake of less than 10 tablets of 10 mg dapagliflozin tablets should not be reported on the eCRF overdose module unless the patient is experiencing a symptomatic overdose. Overdose on IMP will be recorded in the eCRF dosing record module. If an overdose is suspected, monitoring of vital functions as well as treatment should be performed as appropriate.

- An overdose with associated AEs is recorded as the AE diagnosis/symptoms on the relevant AE modules in the eCRF and on the Overdose eCRF module.
- An overdose without associated symptoms is only reported on the Overdose eCRF module.

8.7 Annual safety report

In addition to the expedited reporting of SUSARs, the sponsor will submit, once a year throughout the clinical trial, a safety report to the accredited METC, competent authority, and competent authorities of the concerned Member States.

This safety report consists of:

- a list of all suspected (unexpected or expected) adverse reactions and serious adverse reactions, along with an aggregated summary table of all reported serious adverse reactions, ordered by organ system, per study;
- a report concerning the safety of the subjects, consisting of a complete safety analysis and an evaluation of the balance between the efficacy and the harmfulness of the medicine under investigation.

All safety reports should be simultaneously communicated to Astra Zeneca.

8.8 Data Safety Monitoring Board (DSMB) / Safety Committee]

The institution of a DSMB is not a prerequisite to improve the safety of the patients as the safety profile of dapagliflozin has been well characterized and investigated in completed clinical trials that involved >6000 patients with type 2 diabetes. Dapagliflozin is registered for clinical use in Europe.

9. STATISTICAL ANALYSIS

9.1 Primary study parameter(s)

The log-transformed 24-hour proteinuria values will be analyzed by a Proc Mixed statement in SAS with sequence, treatment, and period as fixed factors and patients (nested in sequence) as a random factor. A contrast statement will be used to determine difference among treatment groups. Statistical analyses will be conducted with SAS version 9.4.

9.2 Secondary study parameter(s)

The change in secondary outcomes, GFR, systolic blood pressure, and neurohormones will be analyzed by a Proc Mixed statement in SAS with sequence, treatment, and period as fixed factors and patients (nested in sequence) as a random factor. Statistical analyses will be conducted with SAS version 9.4.

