5.1. Analysis of primary outcome

The log-transformed 24-hour proteinuria values will be analyzed by a mixed-effects general linear regression model with treatment and period as fixed factor and patients (nested in sequence) as a random factor. This type of model, which accounts for repeated observations within individuals (measurement occasion at level one, individuals at level two) will allow us to estimate the treatment effect (estimated by restricted maximum likelihood). We will also explore the period-specific treatment effect adding in the model the interaction between the treatment and period covariates. If the baseline characteristics will be considerably different across the three regions included (Malaysia, North America, Europe) we shall consider to include region as a layer in the multilevel model fitted or as fixed effect covariate. We will also analyse the log-transformed 24-hour albuminuria values (a specific protein using the same model as described above).

The change in secondary outcomes, mGFR, eGFR, body weight and systolic blood pressure will be analyzed by the same model as showed for the proteinuria outcome.

In general, the models employed will be:

$$y_{it} = \beta_{0i} + \beta_1 Treat_{it} + \beta_2 Period_{it} + \beta_3 Interaction + \varepsilon_{it}$$

$$\beta_{0i} = \beta_0 + u_{0i}$$

$$\varepsilon_{it} \sim N(0, \sigma_\varepsilon^2)$$

Where y_{it} is the outcome for the individual i at time point t , β_{0i} is the intercept for individual i comprised of a sample-average fixed effect β_0 and an individual effect u_{0i} and ε_{it} is the residual error.

Complete case analyses, that is analysing records that present the whole set of information (outcome and covariates) for every visit of the patients will be performed. Patterns of missing data (for the outcomes and the covariates) will be reported. If the proportion of missing records is higher than 5% and/or we will suspect of particular missing mechanisms we will impute the missing values by multiple imputation using the full conditional specification.

Further, if there will be baseline measurements that are missing we will use the values measured at the screening visit: we will document the frequency of this imputation.

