Variables during follow-up	Group 1 (N=xxx)	Group 2 (N=xxx)	Overall (N=xxx)
Vital signs, BP, Biomarkers:			
Week0			
N Mean (SD)	XXX XXX XXX	XXX XXX XXX	XXX XXX XXX
Week3 (if applicable)			
N Mean (SD)	XXX XXX XXX	XXX XXX XXX	XXX XXX XXX
Week6			
N Mean (SD)	XXX XXX XXX	XXX XXX XXX	XXX XXX XXX
Week12			
N Mean (SD)	XXX XXX XXX	XXX XXX XXX	XXX XXX XXX
Week15 (if applicable)			
N Mean (SD)	XXX XXX XXX	XXX XXX XXX	XXX XXX XXX
Week18			
N Mean (SD)	XXX XXX XXX	XXX XXX XXX	XXX XXX XXX
Week24			
N Mean (SD)	XXX XXX XXX	XXX XXX XXX	XXX XXX XXX

Table 4: Descriptive results for primary outcome by visits

Variables during follow-up	Group 1 (N=xxx)	Group 2 (N=xxx)	Overall (N=xxx)
Primary outcome:			
Week0			
N Mean (SD)	xxx xxx xxx	xxx xxx xxx	xxx xxx xxx
Week3 (if applicable)			
N Mean (SD)	xxx xxx xxx	xxx xxx xxx	xxx xxx xxx
Week6			
N Mean (SD)	xxx xxx xxx	xxx xxx xxx	xxx xxx xxx
Week12			
N Mean (SD)	xxx xxx xxx	xxx xxx xxx	xxx xxx xxx
Week15 (if applicable)			
N Mean (SD)	xxx xxx xxx	xxx xxx xxx	xxx xxx xxx
Week18			
N Mean (SD)	xxx xxx xxx	xxx xxx xxx	xxx xxx xxx
Week24			
N Mean (SD)	xxx xxx xxx	xxx xxx xxx	xxx xxx xxx

Table 5: Descriptive results for secondary outcomes by visits

Variables during follow-up	Group 1 (N=xxx)	Group 2 (N=xxx)	Overall (N=xxx)
Secondary outcome:			
Week0			
N Mean (SD)	xxx xxx xxx	xxx xxx xxx	xxx xxx xxx
Week3 (if applicable)			
N Mean (SD)	xxx xxx xxx	xxx xxx xxx	xxx xxx xxx
Week6			
N Mean (SD)	xxx xxx xxx	xxx xxx xxx	xxx xxx xxx
Week12			
N Mean (SD)	xxx xxx xxx	xxx xxx xxx	xxx xxx xxx
Week15 (if applicable)			
N Mean (SD)	xxx xxx xxx	xxx xxx xxx	xxx xxx xxx
Week18			
N Mean (SD)	xxx xxx xxx	xxx xxx xxx	xxx xxx xxx
Week24			
N Mean (SD)	xxx xxx xxx	xxx xxx xxx	xxx xxx xxx

Table 6: Treatment effect for primary outcome

Primary outcome	Dapa (N=xxx)	Placebo (N=xxx)	Difference (Dapa – Placebo) (N=xxx)	p-value
Primary outcome:				
Change from baseline in overall				
N Mean (SD)	xxx xxx xxx	xxx xxx xxx	xxx xxx xxx	xxx
Change from baseline in period 1				
N Mean (SD)	xxx xxx xxx	xxx xxx xxx	xxx xxx xxx	xxx
Change from baseline in period 2				
N Mean (SD)	xxx xxx xxx	xxx xxx xxx	xxx xxx xxx	xxx

Table 7: Treatment effect for secondary outcomes

Secondary outcomes	Dapa (N=xxx)	Placebo (N=xxx)	Difference (Dapa – Placebo) (N=xxx)	p-value
Secondary outcomes:				
Change from baseline in overall				
N Mean (SD)	xxx xxx xxx	xxx xxx xxx	xxx xxx xxx	xxx
Change from baseline in period 1				
N Mean (SD)	xxx xxx xxx	xxx xxx xxx	xxx xxx xxx	xxx

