Change from baseline in period 2				
N Mean (SD)	xxx xxx xxx	xxx xxx xxx	xxx xxx xxx	xxx

Table 8: Treatment effect for primary outcome by pre-specified subgroups

Primary outcome	Dapa (N=xxx)	Placebo (N=xxx)	Difference (Dapa – Placebo) (N=xxx)	p-value
Change from baseline in overall				
Subgroup1				
Yes	xxx xxx xxx	xxx xxx xxx	xxx xxx xxx	xxx
No	xxx xxx xxx	xxx xxx xxx	xxx xxx xxx	xxx
Subgroup2				
Yes	xxx xxx xxx	xxx xxx xxx	xxx xxx xxx	xxx
No	xxx xxx xxx	xxx xxx xxx	xxx xxx xxx	xxx
Subgroup3				
Yes	xxx xxx xxx	xxx xxx xxx	xxx xxx xxx	xxx
No	xxx xxx xxx	xxx xxx xxx	xxx xxx xxx	xxx
Subgroup4				

Yes	XXX XXX XXX	XXX XXX XXX	XXX XXX XXX	XXX
No	XXX XXX XXX	XXX XXX XXX	XXX XXX XXX	XXX
Subgroup XXX				

Figure 1: Patients flow chart based on CONSORT

Figure 2: Primary outcome over time by treatment groups and periods. (

[figure not shown]

Figure 3: Bar charts with changes from baseline to week 6 for primary/secondary outcomes

Figure 4: Process measurements over time

Similar figure as above, but could add more time points in week 3 and week 15.

Figure 5: Forest plot for subgroup analysis for primary outcome

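### The secondary outcomes are analysed as an unadjusted change from an unnamed baseline; if that is each period's own baseline, the GFR and blood pressure contrasts are less precise than the collected data allow

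*Protocol*

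**What the plan says.** - **Primary outcome, Protocol 9.1:** "The log-transformed 24-hour proteinuria values will be analyzed by a Proc Mixed statement in SAS with sequence, treatment, and period as fixed factors", with patient as a random factor. The response is the values.
- **Secondary outcomes, Protocol 9.2:** "The change in secondary outcomes, GFR, systolic blood pressure, and neurohormones will be analyzed by a Proc Mixed statement in SAS", with the same fixed factors and random patient. The response is a change. No baseline is named and no baseline covariate is listed.
- **SAP 5.1:** "The change in secondary outcomes, mGFR, eGFR, body weight and systolic blood pressure will be analyzed by the same model" that is given for proteinuria. The equation defines its response only as the outcome of a patient at a time point.
- **SAP section 5:** base-case treatment effects are unadjusted except for period.
- **SAP section 7:** the shell headed "Table 7: Treatment effect for secondary outcomes" has an overall row and the rows "Change from baseline in period 1" and "Change from baseline in period 2". Table 2 sets out baselines by group and by period. Figure 3 is to show changes over the six weeks from baseline.
- **Visit schedule (Protocol section 3, Time and Events Table, and 7.3):** iohexol GFR is measured at weeks 0, 6, 12, 18 and 24. The week 0 and week 12 measurements precede dosing.

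**The concern.** A random patient effect suits values: the patient's stable level cancels when the two periods are compared. If the response is instead week 6 minus week 0 and week 18 minus week 12, the subtraction has already removed that stable level. The comparison between periods then removes less, and each period carries the error of a second measurement. Subtraction also forces a slope of 1 on the baseline, whereas a fitted slope uses only as much of the baseline as it predicts.

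What is at stake is precision on the outcomes next to proteinuria. Iohexol GFR is the first secondary objective, and an acute fall in GFR is part of the stated hypothesis. The sample size is set for proteinuria alone, so the precision of the GFR result depends on the analysis chosen for it.

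**Working it through.** **The plan's own figure.** Protocol 3.4 gives 50 completers for 80% power at a log difference of 0.288, by a paired t-test with two-sided alpha 0.05. With 0.7 as the SD of the within-patient difference, the noncentral t needs 49, and 50 patients give 81.4% power. With 0.475 × √2 = 0.672, it needs 45, and 50 give 84.4%. For dropout, 50/0.95 = 52.6, so 53. The calculation reproduces. It concerns proteinuria, which Protocol 9.1 analyses as log values, so the point here does not touch it.

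**Inputs for the secondary outcomes.** The documents give no variance, correlation or effect size for GFR or blood pressure, so only variance ratios can be computed, over an assumed range. Let B1, Y1, B2, Y2 be the measurements at weeks 0, 6, 12 and 18: a patient effect plus deviations of unit variance.

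**AR(1) deviations**, with correlations r, r² and r³ at 6, 12 and 18 weeks:

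- Values: Var(Y1 − Y2) = 2(1 − r²).
- Change from period baseline: Var[(Y1 − B1) − (Y2 − B2)] = 4 − 2r − 4r² + 2r³ = 2(2 − r)(1 − r²).
- Values adjusted for the baseline difference: Cov(Y1 − Y2, B1 − B2) = r(1 − r²) and Var(B1 − B2) = 2(1 − r²), so the best slope is r/2. The residual variance is 2(1 − r²) − r²(1 − r²)/2 = (1 − r²)(4 − r²)/2.
- Change against adjusted values: 2(2 − r) ÷ [(4 − r²)/2] = 4/(2 + r).
- Change against unadjusted values: 2 − r.

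| r | Variance ratio, change vs adjusted | SE ratio | Equivalent completers, 50(2 + r)/4 | Variance ratio, change vs unadjusted values |
|---|---|---|---|---|
| 0 | 2.00 | 1.41 | 25 | 2.00 |
| 0.3 | 1.74 | 1.32 | 29 | 1.70 |
| 0.5 | 1.60 | 1.26 | 31 | 1.50 |
| 0.7 | 1.48 | 1.22 | 34 | 1.30 |
| 0.9 | 1.38 | 1.17 | 36 | 1.10 |

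The formula takes the slope as known. Simulation with 50 patients (25 per sequence, 6,000 runs per value of r) gave 1.97, 1.75, 1.56, 1.45 and 1.34 for change against adjusted values, so estimating the slope costs little.

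As an illustration, take an effect that the adjusted analysis would detect with 80% power (1.96 + 0.84 = 2.80). Change scores would detect it with power Φ(2.80/√ratio − 1.96): 51% at r = 0, 60% at r = 0.5 and 66% at r = 0.9.

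**Patient-by-period variation.** Now let a share f of the within-patient variance be common to both measurements of a period, the rest being independent. The variances are 2 for values, 4(1 − f) for change and 2(1 − f²) for adjusted values.

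| f | Change vs unadjusted values, 2(1 − f) | Change vs adjusted, 2/(1 + f) |
|---|---|---|
| 0 | 2.00 | 2.00 |
| 0.25 | 1.50 | 1.60 |
| 0.5 | 1.00 | 1.33 |
| 0.75 | 0.50 | 1.14 |
| 0.9 | 0.20 | 1.05 |

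Unadjusted values lose their advantage at f = 0.5 and are worse than change above it. Adjusted values are better than change throughout.

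**One common baseline.** (Y1 − B) − (Y2 − B) = Y1 − Y2, so the ratio against unadjusted values is exactly 1.

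**The case against.** **The baseline is not stated.** A reader might infer that the plan certainly uses period baselines and so discards up to half of the information on GFR. The documents do not support that. Table 6 has the same change rows for the primary outcome, which is modelled as values, so the rows of Table 7 cannot by themselves settle the response. SAP 5.1 says the secondary outcomes "will be analyzed by the same model as showed for the proteinuria outcome", and SAP 5.3 assesses change through contrasts of a longitudinal model. *Change* could mean a contrast rather than a precomputed difference, or a change from randomization. This objection stands, so the loss has to be stated conditionally.

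**The size is not known.** A doubling is the limit at r = 0, and unadjusted values are not always better than change. This also stands, and it is why the remedy is baseline adjustment and not values alone.

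**Bias and type I error.** A reader might go further and infer bias, or an inflated type I error. If 10% of the effect remained at week 12 and none at week 18, the change contrast would overstate the effect by (1.10 + 1.00)/2 − 1 = 5%. But if a shift persisted equally at both weeks, subtracting the week 12 baseline would remove it, while values alone would keep it. The simulated type I error was 5.4 to 6.5% with the patient variance bounded at zero, a small effect that depends on that bound. Nor does the random patient factor necessarily have nothing to estimate: patient-specific decline would make a patient's two changes positively correlated. None of these is a main concern.

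**It is only precision on secondary outcomes.** With complete wash-out, a period-specific change is still a valid comparison. That is true, and it limits the weight of the point. It is not a reason to keep the less precise analysis when the baselines are already collected.

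**Conclusion.** The point holds in conditional form. The plan analyses a change whose baseline is undefined and does not adjust for baseline. Period-specific baselines are the likeliest reading but are not stated.

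On that reading, with AR(1) deviations and r from 0 to 0.9, the contrast variance is 2.0 to about 1.4 times that of a baseline-adjusted analysis, so the standard error is 41% to 17% larger. With patient-by-period variation instead, the ratio runs from 2.00 at f = 0 to 1.05 at f = 0.9. In no structure computed were change scores more precise than adjusted values. If the change is from one randomization baseline, nothing is lost against unadjusted values. The covariance structures and the values of r and f are assumptions, so the actual loss cannot be fixed from the documents.

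The primary outcome and its sample size are unaffected. This is an inexpensive gain in precision for the secondary outcomes, not a threat to the trial's main conclusion.

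**What to change.** In Protocol 9.2, SAP 5.1 and SAP Table 7:

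1. Define the response for mGFR, eGFR, blood pressure and body weight as the end-of-period values (weeks 6 and 18), with treatment, period and random patient.
2. Add the period baseline (week 0 or 12) and the patient's mean baseline as covariates, so that only the within-patient difference in baselines adjusts the treatment contrast.
3. Take the Table 7 difference, confidence interval and p-value from this model.
4. Keep change from the period baseline, named as such, as a descriptive row or sensitivity analysis. It is a useful check because the week 12 baseline follows the first treatment, so both analyses rely on the wash-out but use that baseline with different weight.

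The cost is wording plus one or two degrees of freedom. The period baselines are already in the visit schedule. The change should be made before unblinding.

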9.3 Other study parameters

Descriptive statistics will be used to analyse the means and distribution between all the study variables. The means of the normal distributed variables will be compared with the student T-test and non-parametric tests (Mann-Whitney U-test for continued and Chi-Square test for nominal variables) will be used for the variables that do not follow a normal distribution. Missing values will be imputed using multiple imputation techniques. Before introducing multiple imputation techniques the pattern of missing values will be examined. If the pattern of missing values indicate that missing values occur randomly a PROC MI statement in SAS will be implemented to impute missing values.

In case patients require rescue medication this will be recorded in the database. During the data-analysis sensitivity analyses will be conducted by adding an additional covariate in the mixed model to account for rescue medication required during the study.

9.4 Interim analysis

N/A

10. ETHICAL CONSIDERATIONS

10.1 Regulation statement

The study will be conducted according to the principles of the Declaration of Helsinki (Fortaleza, 2013) and in accordance with the Medical Research Involving Human Subjects Act (WMO). The Medical Ethical Committee of all participating centers will approve the study.

10.2 Recruitment and consent

Patients will be enrolled to the trial from centers in the Netherlands, Canada, and Malaysia. Prior to their visit to the outpatient clinic, patients will be invited to participate in the study by verbal invitation when they attend the clinic or by sending an invitation letter. In this letter, patients will find a full explanation of the study, advantages and disadvantages of participating, and contact information of the research team members working on this study. Moreover, the letter contains contact information of an independent physician, to whom subjects can address questions about the research before, during and after a study. The patients will be given 2 weeks to consider their decision and will then be asked to sign their written informed consent before they take part in the study.

10.3 Objection by minors or incapacitated subjects (if applicable)

No minors or incapacitated adults will be included in this study

10.4 Benefits and risks assessment, group relatedness

There are no direct benefits for the patients to be included. Participation in the study is on a free-will base. Patients will receive restitution of all costs of transportation. Patients will not receive priority for treatment of other diseases in the clinic during this study. The risks associated with the use of dapagliflozin in patients with non-diabetic kidney disease are considered low. First, dapagliflozin has been used in non-diabetic individuals in doses up to 500 mg/day without reports of adverse events. Secondly, safety data in patients with diabetic kidney disease has been generated in phase 3 trials and demonstrated no additional side effects compared to type 2 diabetes patients without kidney disease. Given the SGLT2i mode of action no further safety issues are anticipated in non-diabetic CKD patients as compared to generally more vulnerable diabetic kidney disease patients included in the past phase 3 studies.

Participation in the proposed study is accompanied with only minor risks. The blood samples will be drawn by means of venipuncture that will be performed during the visit to

the outpatient clinic. All further performed measurements are non-invasive and therefore only minor risks are associated with participation.

10.5 Compensation for injury

The sponsor has a liability insurance which is in accordance with article 7, subsection 6 of legal requirements in the Netherlands (Article 7 WMO). This insurance applies to all participating sites in the Netherlands. An additional liability insurance has been arranged for the participating sites in Canada and Malaysia.

The sponsor University Medical Center Groningen (UMCG) has an insurance for all participating sites in the Netherlands, which is in accordance with the legal requirements in the Netherlands (Article 7 WMO and the Measure regarding Compulsory Insurance for Clinical Research in Humans of 23th June 2003). This insurance provides cover for damage to research subjects through injury or death caused by the study. The insurance applies to the damage that becomes apparent during the study or within 4 years after the end of the study. All patients will receive written information about this insurance.

For the participating sites in Canada and Malaysia the sponsor has another insurance to cover damage to research subjects in these countries. This insurance policy is in accordance with the legal requirements in Canada and Malaysia.

10.6 Incentives (if applicable)

Participation of patients in the study is a free-will decision. Patients will receive restitution of all costs for transportation. Patients do not receive priority for treatment of other diseases in the clinic during this clinical trial.

11. ADMINISTRATIVE ASPECTS, MONITORING AND PUBLICATION

11.1 Handling and storage of data and documents

A subject identification code list will be made to link the data to the subject in order to be able to trace data to an individual subject. This code will not be based on the patient initials and birth-date. The key to the code will be safeguarded by the investigator since the data will be kept for a period of 15 years. The handling of personal data will comply with privacy laws, legislation, codes and/or guidelines that apply in the applicable jurisdictions the study is conducted.

